# 8.11 Visit Requirements

Visit requirements are outlined in Section 1.3. Specific procedure-related details are provided in Section 8.

### 8.11.1 Pre-screening (Part 2 only)

For Part 2 of the study, approximately 50 days prior to treatment allocation, potential participants will undergo pre-screening procedures to determine their eligibility based on results of prior local tumor KRAS mutational testing (see Section 8.10.1.1) and on HLA typing (see Section 8.10.1.2).

Pre-screening procedures are to be completed within 21 days prior to screening procedure initiation. Pre-screening procedures may be repeated if needed after consultation with and approval by the Sponsor. Once Part 2 eligibility requirements regarding KRAS mutational status and HLA type are confirmed, potential participants should have screening procedures performed without delay.

## 8.11.2 Screening

Approximately 28 days prior to treatment allocation, potential participants will be evaluated to determine that they fulfill the entry requirements of the study. Screening procedures may be repeated after consultation with the Sponsor. Written consent must be obtained prior to performing any protocol-specific procedure.

Results of a test performed prior to the participant signing consent as part of routine clinical management are acceptable in lieu of a screening test if performed within the specified time frame. Screening procedures are to be completed within 28 days prior to the first dose of study intervention except for the following:

- Laboratory tests are to be performed within 7 days prior to the first dose of study intervention. An exception is hepatitis testing which may be done up to 28 days prior to the first dose of study intervention.
- Evaluation of ECOG is to be performed within 7 days prior to the first dose of study intervention.
- For women of reproductive potential, a urine or serum pregnancy test will be performed within 72 hours prior to the first dose of study intervention. If urine pregnancy results cannot be confirmed as negative, a serum pregnancy test will be required (performed by the local study site laboratory).
- Baseline radiological evaluations must be done within 28 days prior to the first dose of study intervention.
- Archival tumor sample collection may have occurred at any point prior to the first dose of study intervention.

Participants may be rescreened after initially failing to meet the inclusion/exclusion criteria. Results from assessments during the initial screening period are acceptable in lieu of a repeat screening test if performed within the specified time frame and the corresponding inclusion/exclusion criteria is met. Participants who are rescreened will retain their original screening number. Assessments performed as part of the screening evaluations and within 3 days prior to the first dose of study treatment are not required to be repeated on Day 1 of Cycle 1.

## 8.11.3 Treatment Period/Vaccination Visit

Visit requirements are outlined in the SoA. Specific procedure-related details are provided in Section 8.1.

### 8.11.4 End of Treatment/Discontinuation Visit

The End of Treatment/Discontinuation Visit should occur at the time study intervention is discontinued for any reason. If the Discontinuation Visit occurs 30 days from the last dose of study intervention, at the time of the mandatory Safety Follow-up Visit, the Discontinuation

V941-001-08 FINAL PROTOCOL 24-MAR-2022

Visit procedures and any additional Safety Follow-up procedures should be performed. Visit requirements are outlined in Section 1.3. Additional details regarding participant withdrawal and discontinuation are presented in Section 7.

Participants on active treatment with pembrolizumab monotherapy in the post-treatment phase are discontinued and may be enrolled in to a pembrolizumab extension study. Participants in the survival follow-up phase will not be rolled-over.

### 8.11.5 Post-treatment Visit

### 8.11.5.1 Safety Follow-up Visit

The mandatory Safety Follow-up Visit should be conducted approximately 30 days after the last dose of study intervention or before the initiation of a new anticancer treatment, whichever comes first.

All AEs that occur prior to the Safety Follow-up Visit should be recorded (up to 30 days following end of treatment). Participants with an AE of Grade >1 will be followed until the resolution of the AE to Grade 0-1 or until the beginning of a new anticancer therapy, whichever occurs first. SAEs that occur within 120 days of the end of treatment or before initiation of a new anticancer treatment should also be followed and recorded.

## 8.11.5.2 Imaging Follow-up Visit(s)

Participants who discontinue treatment for reasons other than verified PD should continue with imaging assessments per the protocol defined schedule until: (1) PD is verified or further confirmed by the investigator, (2) initiation of a new anti-cancer treatment, (3) death, (4) withdrawal of consent, or (5) study conclusion or early termination, whichever occurs first.

## 8.11.5.3 Survival Follow-up Visits

Participants, who experience confirmed disease progression or start a new anticancer therapy will move into the Survival Follow-Up Phase and should be contacted by telephone every 12 weeks to assess for survival status until death, withdrawal of consent, or the end of the study, whichever occurs first.

The Sponsor may request survival status be assessed at additional time points during the course of the study. For example, these additional time points may be requested prior to an efficacy interim analysis, and/or final analysis. All participants who are not known to have died prior to the request for these additional survival status time points will be contacted at that time.

Participants on active treatment with pembrolizumab monotherapy in the post-treatment phase are discontinued and may be enrolled in to a pembrolizumab extension study. Participants in the survival follow-up phase will not be rolled-over.

#### 8.11.6 Survival Status

To ensure current and complete survival data is available at the time of database locks, updated survival status may be requested during the course of the study by the Sponsor. For example, updated survival status may be requested prior to but not limited to an external Data Monitoring Committee (eDMC) review, interim and/or final analysis. Upon Sponsor notification, all participants who do not/will not have a scheduled study visit or study contact during the Sponsor defined time period will be contacted for their survival status (excluding participants that have a previously recorded death event in the collection tool).

### 9 STATISTICAL ANALYSIS PLAN

This section outlines the statistical analysis strategies and procedures for the primary and secondary analyses of the study. Exploratory and other nonconfirmatory analyses will be outlined in a separate supplemental Statistical Analysis Plan (sSAP).

If, after the study has begun, changes are made to primary and/or secondary objectives, or the statistical methods related to those objectives, then the protocol will be amended (consistent with ICH Guideline E9). Changes to exploratory or other nonconfirmatory analyses made after the protocol has been finalized, but prior to the conduct of any analyses, will be documented in the sSAP as needed and referenced in the Clinical Study Report (CSR) for the study. Post hoc exploratory analyses will be clearly identified in the CSR.

# 9.1 Statistical Analysis Plan Summary

Full details are in the Statistical Analysis Plan (SAP), Sections 9.2 to 9.12.

Study Design Overview	Phase 1 trial of mRNA-5671/V941 monotherapy (Arm A) and mRNA-5671/V941 in combination with pembrolizumab (Arm B) in participants with advanced/metastatic solid tumors. The study applies a modified TPI design for dose finding.
Treatment Assignment	Participants will be allocated centrally through IVRS/IWRS to single agent mRNA-5671/V941 and mRNA-5671/V941 coadministered with pembrolizumab.
Analysis Populations	Safety (Primary): All-Subjects-as-Treated (AsaT) Pharmacodynamic (Secondary): Per-Protocol (PP) Efficacy (Secondary and Exploratory): Full Analysis Set (FAS)
Primary Endpoint(s)	
 
Dose-limiting toxicity (DLT)
 
Adverse event (AE)
 
Discontinuing study treatment due to an AE
 

Secondary Endpoints	
 
Objective response is a confirmed CR or PR.
 
Presence of and changes in the quantity of mutant KRAS-specific T cells in the blood.
 

Statistical Methods for Efficacy/ Immunogenicity/	ORR in participants treated with mRNA-5671/V941 monotherapy (Arm A) and mRNA-5671/V941 in combination with pembrolizumab (Arm B) will be estimated using an exact method based on the binomial distribution (Clopper-

Pharmacokinetic Analyses	Pearson interval) together with its 95% confidence interval.  Methods for the rest of the efficacy analyses are documented in the sSAP.  Summary statistics will be provided for the immunogenicity parameters.
Statistical Methods for Safety Analyses	Summary statistics will be provided for the safety endpoints as appropriate. The pool-adjacent-violators-algorithm [Ji Y, Li Y, Bekele BN 2007] will be used to estimate the DLT rates across doses. The estimate of the DLT rate among participants treated at RP2D of mRNA-5671/V941 and the 80% Bayesian credible intervals for the estimate will be provided for each treatment arm.
Interim Analyses	An interim analysis for part 2 will be conducted after about 60% of enrollment in each tumor cohort.
Multiplicity	No multiplicity adjustment is planned in this Phase 1 trial.
Sample Size and Power	The overall sample size for this study depends on the observed DLT profiles of mRNA-5671/V941 monotherapy and mRNA-5671/V941 in combination with pembrolizumab. A target sample size of 100 participants will be used for study planning purposes.

# 9.2 Responsibility for Analyses/In-house Blinding

The statistical analyses of the data obtained from this study will be the responsibility of the Clinical Biostatistics department of the Sponsor.

The trial is open-label, ie, participants, investigators, and Sponsor personnel will be aware of participant treatment assignment after each participant is enrolled and treatment is assigned. Allocation to treatment will not be randomized.

## 9.3 Hypotheses/Estimation

Objectives and hypotheses of the study are outlined in Section 3 – Objectives/Hypotheses and Endpoints.

### 9.4 Analysis Endpoints

# 9.4.1 Efficacy/Immunogenicity Endpoints

Objective response rate is the secondary endpoint in this study. Objective response rate is defined as the proportion of participants in the analysis population who experience complete response (CR) or partial response (PR) using RECIST 1.1 criteria as assessed by investigator review.

Other efficacy endpoints (eg, PFS, OS) are exploratory endpoints in this trial and details of the analysis plan will be documented in the sSAP. Progression-free survival (PFS) is defined as the time from the first dose of study medication to the first documented disease progression (PD), using RECIST 1.1 criteria as assessed by investigator review, or death due to any cause, whichever occurs first. Overall survival (OS) is defined as the time from the

first dose of study medication to death due to any cause. Participants who did not die will be censored on the date of last study assessment or contact.

107

Immunogenicity endpoints may include the following: 1) Presence of and changes in the quantity of mutant KRAS-specific T cells in the blood and 2) TCR clonality and diversity in the blood.

# 9.4.2 Safety Endpoints

The primary safety endpoint is the incidence of DLTs. In addition, safety and tolerability will be assessed by clinical review of all relevant parameters including AEs, laboratory tests, and vital signs.

A description of safety measures is provided in Section 8.3 – Safety Assessments.

## 9.5 Analysis Populations

## 9.5.1 Safety Analysis Populations

The All-Subjects-as-Treated (AsaT) population will be used for the analysis of safety data in this study. The AsaT population consists of all participants who received at least 1 dose of study treatment.

The DLT evaluable population includes AsaT participants that meet the criteria for DLT evaluability (eg, finished Cycle 1 without a DLT or experienced a DLT in Cycle 1). See Section 6.6.2 for details.

At least 1 laboratory or vital sign measurement obtained subsequent to at least 1 dose of study treatment is required for inclusion in the analysis of each specific parameter. To assess change from baseline, a baseline measurement is also required.

Data from participants who crossover from monotherapy to the combination therapy will be presented separately.

### 9.5.2 Pharmacokinetic/Immunogenicity Analysis Populations

The Per-Protocol (PP) population will be used for the analysis of PK and immunogenicity data in this study. The PP population consists of the subset of participants who complied with the protocol sufficiently to ensure that their data will be likely to exhibit the effects of treatment, according to the underlying scientific model. Compliance includes such considerations as exposure to treatment, availability of measurements, and the absence of major protocol violations. Any participants or data values excluded from the analyses will be identified, along with the reasons for exclusion, in the CSR. At the end of the study, all participants who were compliant with the study procedures and have available data from at least 1 treatment will be included in the PP analysis dataset.

# 9.5.3 Efficacy Analysis Populations

The Full Analysis Set (FAS) population will be used for the analyses of secondary and exploratory efficacy data in this study. It consists of participants with centrally-confirmed tumor KRAS mutations, with a baseline scan that demonstrated measurable disease by the investigator's assessment, and who were administered at least 1 dose of study medicine. Participants from the dose finding phase in the combination arm (Arm B) who are treated at the RP2D and meet the dose expansion eligibility criterion will be pooled together with participants enrolled in the dose expansion in a supportive analysis.

Data from participants who crossover from monotherapy to the combination therapy will be presented separately.

## 9.6 Statistical Methods

This section describes the statistical methods that address the primary and secondary objectives. Methods related to exploratory endpoints will be described in the sSAP.

# 9.6.1 Statistical Methods for Safety Analysis

Safety and tolerability will be assessed by clinical review of all relevant parameters including AEs, SAEs, laboratory tests, vital signs, ECG measurements, and physical examinations.

Adverse events will be summarized by counts and frequencies for each dose level. Laboratory tests, vital signs, and other safety endpoints will be summarized as appropriate.

Dose limiting toxicities will be listed and summarized by dose level. The pool adjacent violators-algorithm [Ji Y, Li Y, Bekele BN 2007], which forces the DLT rate estimates to be nondecreasing with increasing dose levels and pools adjacent violators for weighted estimates by sample size, will be used to estimate the DLT rates across doses in each treatment arm. The estimate of the DLT rate among participants treated at the RP2D and the 80% Bayesian credible interval based on a prior distribution of Beta (1,1) for the estimate will be provided.

# 9.6.2 Statistical Methods for Efficacy Analysis

ORR, along with the confidence interval, will be estimated using an exact method based on the binomial distribution (Clopper-Pearson method). The statistical methods for other efficacy endpoints are exploratory nature and will be documented in the sSAP.

# 9.6.3 Summaries of Baseline Characteristics, Demographics, and Other Analyses

# 9.6.3.1 Demographic and Baseline Characteristics

Demographic variables, baseline characteristics, primary and secondary diagnoses, and prior and concomitant therapies will be summarized.

# 9.6.3.2 Pharmacokinetic and Pharmacodynamic Modeling Analysis

Pharmacokinetic parameters of pembrolizumab will be summarized by planned visit and time for each dose separately.

Pharmacokinetics and pharmacodynamics modeling analyses will be documented in the sSAP.

# 9.7 Interim Analyses

Due to low prevalence of KRAS mutant and selected HLA typing population, the accrual is expected to be slow. A futility analysis will be conducted after about 60% of enrollment in each tumor cohort. For example, if no response is observed among the 9 participants in the non-MSI-H CRC or pancreatic cohort, or less than 7 responses out of 24 participants in the NSCLC cohort, enrollment to the tumor cohort may be stopped. The totality of data across the cohorts will be assessed to stop the trial early for futility.

# 9.8 Multiplicity

There will be no multiplicity control in this study.

# 9.9 Sample Size and Power Calculations

The planned total sample size for Part 1 dose finding is approximately 30 participants. The actual sample size could be less given that the therapeutic vaccine is expected to have a tolerable toxicity profile. The planned sample size for Part 2 efficacy expansion is 70 participants (40 for NSCLC, 15 for non-MSI-H CRC and 15 for pancreatic).

While there is no formal hypothesis testing in this study, preliminary efficacy in the Part 2 expansion will be assessed with the pruning and pooling method [Chen, C., et al 2016]. With 70 participants by the aforementioned allocation, the study has approximately 83% power for detecting a 15% improvement of ORR over historical control (pembrolizumab monotherapy) in at least 1 of the 3 tumor indications, while controlling the Type I error for the global null hypothesis under 5%. The ORR for historical control in the KRAS mutated population is assumed to be 1% for non-MSI-H CRC, 1% for pancreatic adenocarcinoma, and 20 to 25% for NSCLC.

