In Part 2, participants with advanced solid tumors who have received various prior lines of therapy will be enrolled into each of the following 3 expansion cohorts for the following tumor types: 40 participants with advanced/metastatic NSCLC, 15 participants with non-MSI-H CRC, and 15 participants with pancreatic adenocarcinoma. Participants must have tumor KRAS G12D, G12V, G13D, or G12C mutations, as determined by local testing, and must also have confirmed HLA types HLA-A11:01 and/or HLA-C08:02 (and/or potentially other additional HLA types to be specified in the Procedures Manual). Part 2 will further evaluate safety and efficacy of mRNA-5671/V941 in combination with pembrolizumab at the mRNA-5671/V941 RP2D defined in Part 1 Arm B.

The final RP2D for future studies will be confirmed using all available safety information (including early and late toxicities from Parts 1 and 2), as well as immunogenicity and pharmacodynamic data, and preliminary efficacy assessments.

Participants on active treatment with pembrolizumab monotherapy in the post-treatment phase are discontinued and may be enrolled in to a pembrolizumab extension study. Participants in survival follow-up phase will not be rolled-over.

Preliminary efficacy will be evaluated using objective response rate (ORR) assessed by the investigator based on the Response Evaluation Criteria In Solid Tumors version 1.1 (RECIST 1.1) as a secondary objective. Progression-free survival (PFS) based on RECIST 1.1 as assessed by the investigator and overall survival (OS) will be evaluated as exploratory objectives. ORR and PFS will be also assessed by modified Response Evaluation Criteria in Solid Tumors 1.1 for immune-based therapeutics (iRECIST).

Participants will be monitored carefully for the development of adverse events AEs, and for clinical and/or radiographic evidence of disease progression according to RECIST 1.1. However, iRECIST may be used by the investigator for treatment decisions. In participants who have initial evidence of radiological progressive disease by RECIST 1.1, it will be at the discretion of the investigator whether to continue a participant on study treatment until repeat

Confidential

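### Do the unstated pooling rule and the 20 to 25% NSCLC reference rate in Section 9.9 undermine the Part 2 response analysis?

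*Combined protocol and SAP*

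**What the plan says.** Section 9.9 plans 70 participants in Part 2: 40 NSCLC, 15 non-MSI-H CRC and 15 pancreatic. It disclaims formal hypothesis testing, then says "preliminary efficacy in the Part 2 expansion will be assessed with the pruning and pooling method", citing a published basket-trial paper for the method. It claims "approximately 83% power for detecting a 15% improvement of ORR over historical control (pembrolizumab monotherapy) in at least 1 of the 3 tumor indications", with the error rate under the global null held below 5%. The assumed historical ORRs are 1% for CRC, "1% for pancreatic adenocarcinoma, and 20 to 25% for NSCLC".

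Section 9.6 opens with "This section describes the statistical methods that address the primary and secondary objectives". ORR is a secondary endpoint, and under Section 9.6.2 it "will be estimated using an exact method based on the binomial distribution (Clopper-Pearson method"; Section 9.1 gives the level as 95%. Section 9.6.2 adds: "The statistical methods for other efficacy endpoints are exploratory nature and will be documented in the sSAP". The opening of Section 9 sends exploratory and other nonconfirmatory analyses to the supplemental SAP (sSAP), and Section 9.1 sends the remaining efficacy analyses there.

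Section 9.7 offers example futility bars at about 60% enrolment: no responses in 9 for CRC or pancreatic, fewer than 7 in 24 for NSCLC. Under Section 4.1 the final RP2D draws on all safety information "as well as immunogenicity and pharmacodynamic data, and preliminary efficacy assessments". Section 9.2 says "participants, investigators, and Sponsor personnel will be aware of participant treatment assignment".

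**The concern.** Section 9.9 names an analysis method that the methods section does not mention. The supplied text gives no final pruning bar, pooled statistic, critical value or single NSCLC rate, and does not say which tumour types are active in the power calculation. Because the sponsor sees responses as they accrue, the reference rate and the reading rule could in principle be chosen afterwards.

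The choice of rate would bite where the design aims. A 15-point gain over 20% is 14 of 40, and over 25% it is 16 of 40. Both counts, and 15 between them, would look like a gain against 20% but not clearly against 25%. NSCLC supplies 40 of the 70 participants. A reader might also take 83% as the chance of detecting one responsive tumour type.

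**Working it through.** **Inputs.** Cohort sizes 40/15/15; reference ORRs of 20 or 25% (NSCLC) and 1% (CRC, pancreatic); a gain of 15 percentage points, read as absolute; global error below 5%, taken as one-sided (all Section 9.9). Confidence level 95%, taken as two-sided (Section 9.1). Interim bars 7/24 and 1/9 (Section 9.7).

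**1. Can the 83% be reached?** The inputs are incomplete, so a version has to be assumed. Drop a cohort that misses its Section 9.7 bar. Sum the responses X over the cohorts that remain and form z = (X − Σn·p0) / √(Σn·p0(1 − p0)). Choose the critical value so that the exact error under the global null is at most 5%.

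| Cohorts with a 15-point gain | NSCLC rate 20% (z ≥ 2.286, exact error 4.0%) | NSCLC rate 25% (z ≥ 2.399, exact error 2.8%) |
|---|---|---|
| All three | 93.9% | 88.8% |
| NSCLC and one small cohort | 83.8% | 73.9% |
| Both small cohorts | 85.8% | 74.1% |
| NSCLC only | 56.1% | 45.6% |
| One small cohort only | 63.2% | 49.7% |

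One natural version lands within a point of the plan's figure. Over all the pruning bars, reference rates and activity patterns tried, power ran from 26% to 98%. The 83% is therefore neither confirmed nor refuted.

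**2. Ceiling with one active type.** If only one cohort departs from its reference rate, the likelihood ratio depends on that cohort alone. The most powerful 5% test is then the randomised binomial test on it: power = P(X ≥ c | p1) + γ·P(X = c − 1 | p1), where γ = [0.05 − P(X ≥ c | p0)] / P(X = c − 1 | p0).

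- NSCLC, 20 vs 35%, n = 40, c = 13: 0.6857 + 0.1527 × 0.1090 = 70.2%.
- NSCLC, 25 vs 40%, n = 40, c = 16: 0.5598 + 0.8426 × 0.1228 = 66.3%.
- CRC or pancreatic, 1 vs 16%, n = 15, c = 2: 0.7179 + 0.3098 × 0.2090 = 78.3%.

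No 5% test reaches 83% with one active type. Section 9.9 does not say that only one is active.

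**3. Effect of the open NSCLC rate.** The lower Clopper-Pearson limit is the 2.5% point of Beta(x, n − x + 1); the upper is the 97.5% point of Beta(x + 1, n − x).

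| NSCLC responses of 40 | 95% interval | Excludes 20%? | Excludes 25%? |
|---|---|---|---|
| 13 | 18.6 to 49.1% | no | no |
| 14 | 20.6 to 51.7% | yes | no |
| 15 | 22.7 to 54.2% | yes | no |
| 16 | 24.9 to 56.7% | yes | no |
| 17 | 27.0 to 59.1% | yes | yes |

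P(14 to 16 responses) is 0.131 + 0.123 + 0.103 = 0.357 at a true ORR of 35%, and 0.106 + 0.123 + 0.128 = 0.357 at 40%. If the 7/24 bar were binding, both would be about 34%. The chance that the interval clears the reference after a true 15-point gain is P(X ≥ 14 | 35%) = 55.9% against 20%, and P(X ≥ 17 | 40%) = 43.2% against 25%.

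The band depends on the yardstick. A one-sided 5% exact test, closer to the error rate in Section 9.9, needs 13 responses against 20% (p = 0.043) and 16 against 25% (p = 0.026), so the band becomes 13 to 15.

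**4. Can the two methods disagree?** Take NSCLC 9/40 and CRC 3/15, with pancreatic stopped. The CRC interval is 4.3 to 48.1%, clear of 1%. An exact test on the total, 12 of 55, gives p = 0.099 (NSCLC 20%) or 0.305 (25%). This needs NSCLC to pass its interim bar. With 9 responses in 40, the hypergeometric chance that at least 7 fall among the first 24 is 20.0%. In the other 80% of orderings the bar would prune NSCLC. Disagreement is possible, but the example is a selected one.

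**The case for a change.** The strongest case for a change is that Section 9.9 says how efficacy will be assessed, which is more than a sample-size remark, and that power and error claims imply a rule. Section 9.6 claims to cover the secondary objectives and does not contain that rule. The Section 9.7 bars are examples, nonbinding, not linked to pooling, and give no final boundary. In an open-label trial, fixing the reference rate and the rule in advance would cost a few sentences and no participants.

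Much of this stands as description. The supplied text does not give the rule, the NSCLC rate or the scenario, and Section 9.6.2 has no cross-reference to Section 9.9. It does not establish a fault in the plan, for four reasons.

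- The opening of Section 9 and Section 9.1 plausibly route a nonconfirmatory pooled assessment to the sSAP, and Section 9.9 cites the method's source. Neither was available, so absence from this text does not show absence from the plan.
- Section 9 requires sSAP changes to be documented before any analyses are conducted and post hoc exploratory analyses to be identified in the CSR. That limits the scope for quiet choices later, if the rule is in the sSAP.
- An interval for each ORR and a global statement about at least one of three types answer different questions. Neither has to govern the other.
- No section compares the Clopper-Pearson interval with 20% or 25%. That comparison, and so the 14 to 16 band, is a reading added from outside.

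**Conclusion.** The concern does not call for a change. The 83% is attainable for the claim as worded, when two or three tumour types are active and depending on the unstated bar and test. No stated figure or rule is shown to be wrong. Writing down the NSCLC rate, the scenario and the pooled rule would alter no ORR estimate, no futility count and no primary DLT or adverse event result, and no better method is at issue.

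The gap is one that analysts can fill sensibly: report NSCLC ORR with its interval, set it beside both 20% and 25%, and do not present 83% as the power for a single responsive type (the ceiling is 66 to 70% for NSCLC, 78% for CRC or pancreatic). Stating the historical rate as a range is open about real uncertainty. Choosing one end is a trade-off: 56% against 43% chance of clearing the reference after a true 15-point gain.

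What hangs on the reading is limited. Part 2 studies the RP2D already defined in Part 1 Arm B, so ORR against 20% or 25% does not discriminate between doses, although preliminary efficacy is one input to confirming the final RP2D.

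These figures assume an absolute 15-point gain, one-sided 5% tests, two-sided 95% intervals, and all 40 NSCLC participants in the Full Analysis Set, which requires centrally confirmed KRAS mutation (Section 9.5.3). The pruned power figures also assume the z statistic above, since the sponsor's own is not in the documents.
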